6.8 Safety Assessments

6.8.1 Adverse Events

All adverse events (AEs) or hypoglycaemia episodes occurring after signing the informed consent are to be recorded on the AE or the hypoglycaemia episode pages of the CRF. Investigators verbatim term of AE and hypoglycaemia episode will be mapped to system organ class (SOC) and preferred term (PT) using MedDRA version 21.0. All hypoglycaemia episodes will be coded as “Hypoglycaemia” (LLT code=10020993, ver21.0).

Duration of adverse events will be derived as:

- $\text{Duration of AE (Days)} = \text{End Date} - \text{Start Date} + 1$

6.8.1.1 Definitions

Treatment Emergent Adverse Events (TEAEs):

TEAEs are defined as any AEs or hypoglycaemia episodes that occur or worsen (increase in severity) on the same day or after randomized.

The following rules will apply in cases where the start date of an AE is known:

- If the AE onset date is prior to Day 1, then the AE will not be considered a TEAE.
- If the AE onset date or date of AE worsening is equal to or later than Day 1, then the AE will be considered a TEAE.

The same rule will be applied in cases where start date of a hypoglycemic episode is known.

Refer [section 7.3.1](#) to identify TEAE status when start date of an AE or hypoglycaemia episodes is unknown.

Adverse Drug Reactions (ADRs):

ADRs are defined as TEAE whose causal relationship to study drug is “Reasonable possibility”. If the causal relationship to study drug is missing, then that TEAE will be treated as ADR.

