6.5 Prior and Concomitant Therapy

6.5.1 Prohibited Concomitant Medications

(1) Anti-diabetic drugs

Concomitant use of the following medications is not permitted within at least 8 weeks before the screening visit until 2 weeks after the final dose of the study drug. Subjects may use the following medications after 2 weeks after the final dose of the study drug including the early termination if required when judged by the investigator: Insulin, sulfonylureas, metformin, alpha-glucosidase inhibitors, thiazolidinediones, Repaglinide, DPP-4 inhibitors, GLP-1 receptor agonists, herbal medicines that lower blood glucose levels, new drugs intended for diabetes, fixed dose combination tablets including above active ingredients.

Subjects can use the anti-diabetic treatment after Early termination visit when the subject discontinues the study due to a lack of glycaemic control.

(2) Others

The following medications are not permitted in the period from the screening visit to 2 weeks after the final dose of the study drug out of a concern for the influence on the efficacy and safety assessment. Subjects may use the following medications after 2 weeks after the final dose of the study drug including the early termination if required when judged by the investigator: Adrenocorticosteroids (excluding for external use) for more than 2 consecutive weeks and other investigational products (including placebo)

Subjects can use the adrenocorticosteroids after Early termination visit when the investigator consider that the treatment is necessary.

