- Review use of concomitant treatments
- Blood and urine is to be drawn and sent to the central laboratory according to the local procedure for evaluation of haematology, clinical chemistry, urinalysis, HbA1c, FPG, fasting insulin, C-peptide and glucagon
- Evaluation for any AEs including hypoglycaemic episodes experienced by the subjects since last visit
- Review subject diary
- MP-513 or placebo will be dispensed to the subjects. Unused medication has to be returned to the site
- Subjects are to be instructed that they have to return for the next scheduled visit day.

Treatment Visit 6 (Week 24 plus/minus 7 days of treatment/Early termination visit: date of discontinuation* plus 7 days)

*Date of discontinuation is defined as the date of decision of discontinuation for subjects by the investigator.

This visit is the regular **end of treatment visit**. In case of premature termination, the same evaluations have to be performed as **the early termination visit**.

The following observations/procedures are to be performed and checked:

- Vital signs, body weight and ECG
- Review use of concomitant treatments
- Blood and urine is to be drawn and sent to the central laboratory according to the local procedure for evaluation of haematology, clinical chemistry, urinalysis and HbA1c, FPG, fasting insulin, C-peptide and glucagon.
- A serum pregnancy test is to be performed in females with childbearing potential.
- Evaluation for any AEs including hypoglycaemic episodes experienced by the subjects since last visit
- Review and final collection of subject diary
- Unused MP-513 or placebo has to be returned to the site.

Follow-up Visit (Week 26 plus 14 days following completion / Early termination of double-blind treatment period)

Two weeks after end of treatment, a telephone follow-up visit will take place to ask the subjects about any AEs including hypoglycaemic episodes experienced by the subjects since the last visit and use of concomitant treatments.

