6 BASELINE, EFFICACY AND SAFETY EVALUATIONS

6.1 Schedule of Evaluations

The assessments to be conducted at each scheduled visit are displayed in the below table.

Table 2 Schedule of Visits

Period	Scr. Period	Placebo Run-in Period		Double-Blind Treatment Period						Follow-up Period
		PV	RV	V1	V2	V3	V4	V5	V6	
Visit	SV	PV	RV	V1	V2	V3	V4	V5	V6	FV
Visiting Windows	Day -28 +/- 3 days	Day -14 +/- 3 days	Day 1	Week 4 +/- 7 days	Week 8 +/- 7 days	Week 12 +/- 7 days	Week 16 +/- 7 days	Week 20 +/- 7 days	Week 24 ⁽⁵⁾ +/- 7 days	Week 26 ⁽⁶⁾ + 14 days
Items										
Obtain written informed consent	X									
Screening/Inclusion/Exclusion criteria evaluation	X	X	X							
Demographics and complete medical history	X ⁽⁷⁾									
Height	X									
Body Weight	X		X	X	X	X	X	X	X	
Vital signs ⁽¹⁾	X	X	X	X	X	X	X	X	X	
12-lead ECG	X		X			X			X	
Routine laboratory evaluations: hematology, chemistry, urinalysis	X		X	X	X	X	X	X	X	
Serum pregnancy test ⁽²⁾	X								X	
HbA1c	X	X	X	X	X	X	X	X	X	
Fasting plasma glucose	X	X	X	X	X	X	X	X	X	
Fasting insulin, C-peptide and glucagon			X	X	X	X	X	X	X	
Dispense medication		X	X	X	X	X	X	X		
Return of unused medication			X	X	X	X	X	X	X	
Assessment of adverse events ⁽³⁾ and concomitant medication	X	X	X	X	X	X	X	X	X	X
Hypoglycaemic episodes ⁽⁴⁾	X	X	X	X	X	X	X	X	X	X
Dispense subjects diary and glucometer	X									
Subject diary review		X	X	X	X	X	X	X	X	

Scr period: Screening period, SV: Screening visit, PV: Placebo run-in visit, RV: Randomization visit, FV: follow-up visit

(1) Vital signs (sitting blood pressure, pulse rate and body temperature)

(2) The serum pregnancy test will be performed only for female subjects of childbearing potential.

(3) AEs will be collected and reported on the eCRF from the date of informed consent to 14 days after the final dose of the study drug considering the half-life (T1/2) of MP-513.

(4) The occurrence of hypoglycaemic episodes will be recorded continuously throughout the study by a subject diary

(5) These assessments will also be performed at early termination.

(6) Telephone visit

(7) Including physical examination

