8.5 Prior and Concomitant Therapy

A full subject listing of prior and concomitant medications will be presented.

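### The treatment-emergent event rule has no end day, so hypoglycaemia on a new anti-diabetic drug after withdrawal for lack of glycaemic control can enter the study arm's all-cause safety rows

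*SAP*

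**What the plan says.** **TEAE rule.** SAP 6.8.1.1 states: "TEAEs are defined as any AEs or hypoglycaemia episodes that occur or worsen (increase in severity) on the same day or after randomized". The rule for known dates, which up to its last word reads "If the AE onset date or date of AE worsening is equal to or later than Day 1, then the AE will be considered a", repeats the lower limit only. SAP 7.3.1, on unknown dates, adds no upper limit.

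**Collection period.** Footnote 3 to the visit schedule (SAP 6.1, and the same table in Protocol 6.6.1) has AEs collected "from the date of informed consent to 14 days after the final dose of the study drug". For hypoglycaemia, SAP 6.8.1 says only that AEs and episodes "occurring after signing the informed consent are to be recorded on the AE or the hypoglycaemia episode pages of the CRF", with no end. The follow-up call in Protocol 6.6.1 asks about "any AEs including hypoglycaemic episodes experienced by the subjects since the last visit and use of concomitant treatments".

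**Other anti-diabetic drugs.** Protocol 6.3.3 withdraws subjects whose fasting glucose exceeds set limits and refers them for other glucose-lowering therapy. Protocol 6.5.1 bans other anti-diabetic drugs until two weeks after the last dose, early termination included, with one exception: "Subjects can use the anti-diabetic treatment after Early termination visit when the subject discontinues the study due to a lack of glycaemic control".

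**Data after withdrawal.** SAP 7.3 says that data from discontinued subjects are summarised up to discontinuation. Protocol 6.6.1 (Treatment Visit 6) dates discontinuation to the investigator's decision and allows up to 7 days from then for the early termination visit.

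**Tables.** SAP 8.8.1 has overview rows for any TEAE, for hypoglycaemia and for study-drug-related hypoglycaemia. Nothing in the SAP text separates events by whether another anti-diabetic drug had been started. For medications, SAP 8.5 offers only this: "A full subject listing of prior and concomitant medications will be presented".

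**The concern.** Hypoglycaemia is a named safety endpoint, and the comparison with placebo is meant to describe MP-513 as monotherapy. The drugs banned during the study include insulin and sulfonylureas. Once a subject has been withdrawn and moved to one of these, an episode in the following days says little about the study treatment. If it is still tabulated under the study arm, the all-cause rows mix two exposures.

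The mixing need not be balanced. The trigger is high fasting glucose, and the study drug is expected to lower glucose, so placebo subjects are the likelier ones to meet it. Extra episodes in the placebo row would make MP-513 look relatively safer on hypoglycaemia. Few episodes are likely on either arm, so one or two misplaced subjects could change how the row reads.

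**Working it through.** The plan states no figure to reproduce. The check is a comparison of the rules, followed by an illustration of scale.

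**1. Do new-drug exposure and event collection overlap?** For lack-of-control withdrawals the new drug is allowed once the early termination visit is done, and AE collection runs to day 14 after the last dose. The overlap is therefore at most 14 days. If dosing stops on the decision date and the visit takes place 7 days later, 14 − 7 = 7 days remain. Other withdrawals stay under the two-week ban, so for them AE collection ends as the ban ends.

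**2. Is hypoglycaemia bounded in the same way?** Not expressly, because the 14-day limit is written for AEs. SAP 6.2.2 places the follow-up call on Days 182–196. With a last dose near Day 168, a call on Day 196 looks back 196 − 168 = 28 days.

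**3. Are the overlapping events counted?**

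| Rule | Result for an episode on the new drug |
|---|---|
| SAP 6.8.1.1 | Onset is after Day 1, so it is a TEAE |
| SAP 7.3, with discontinuation dated to the decision (Protocol 6.6.1) | The drug is allowed only after the early termination visit, which is on or after the decision date. The episode comes after discontinuation and is not summarised |

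On that reading the two sections give opposite answers. The SAP does not define the point of discontinuation and does not link SAP 7.3 to the TEAE rule.

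**4. Which arm?** SAP 8.3 assigns a subject to MP-513 if any MP-513 was taken, and otherwise to the randomised arm.

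**5. How many subjects?** Planned size is 120 per arm (Protocol synopsis). Withdrawal for lack of control and the 14-day hypoglycaemia risk on the new drug are not in the documents; the values below are assumptions.

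- Extra subjects in an arm = 120 × withdrawal share × risk
- Shift in the between-arm difference = (placebo share − MP-513 share) × risk
- Chance of at least one in placebo = 1 − (1 − risk)^(120 × placebo share)

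| Withdrawn, placebo / MP-513 | Risk | Extra placebo | Extra MP-513 | Shift (percentage points) | Chance of ≥1, placebo |
|---|---|---|---|---|---|
| 2% / 0.5% | 1% | 0.02 | 0.01 | 0.015 | 2% |
| 5% / 1% | 5% | 0.30 | 0.06 | 0.20 | 26% |
| 10% / 3% | 5% | 0.60 | 0.18 | 0.35 | 46% |
| 15% / 5% | 10% | 1.80 | 0.60 | 1.00 | 85% |
| 5% / 5% | 5% | 0.30 | 0.30 | 0 | 26% |

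For example, in the fourth row 120 × 0.15 × 0.10 = 1.80, and (0.15 − 0.05) × 0.10 = 1.00 percentage point. One subject is 1/120 = 0.83 percentage points; going from two subjects to three moves a row from 1.7% to 2.5%.

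**The case against.** The strongest reply is that SAP 7.3 already removes these events. That reading is available, so a reader who infers that they are certain to be counted goes further than the documents. But SAP 7.3 is not tied to the TEAE rule. Applied literally from the decision date, it would also drop genuine late events of the study drug, and assessments made at an early termination visit held after that date. It shows a conflict and does not resolve it.

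Second, an episode graded plainly not related to study drug leaves the related-hypoglycaemia row and the adverse drug reaction tables, so it would be wrong to say that nothing filters these events. The filter is partial: gradings of possibly not related or unassessable (Protocol 6.6.2.4) and missing causality (SAP 6.8.1.2) all count as related, and the all-cause row is unfiltered. The table and listing shells named in the SAP contents are not in the text reviewed here, so a split there cannot be ruled out.

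Third, capture in this period is weak. Protocol 6.6.1 makes the early termination visit the last diary review, so later episodes rest mainly on recall at the call. This, together with the high fasting glucose of the subjects concerned, points to the lower part of the range.

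Fourth, counting all events in a fixed post-dose window is a recognised convention, and a cut at new-drug start would make follow-up depend on glycaemic control. This stands, and it is why the all-events count should remain.

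**Conclusion.** The point holds in a limited form. The TEAE definition has no end day. For subjects withdrawn for lack of glycaemic control, a new anti-diabetic drug can overlap with event collection. SAP 6.8.1.1 and SAP 7.3 can be read to give opposite answers on the resulting events.

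Three stronger readings are not supported:

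- **Any withdrawn subject may switch drugs during collection.** The exception in Protocol 6.5.1 covers lack of glycaemic control only.
- **AEs are counted without limit.** Collection stops 14 days after the last dose; what is missing is a link from that limit to the TEAE rule and to hypoglycaemia.
- **The bias is known to be one-sided.** Placebo weighting is a fair inference from the fasting-glucose trigger and from the placebo-subtracted HbA1c effects in Protocol section 4 (−0.79% in the Japanese placebo-controlled study 3000-A5). However, no withdrawal rates by arm are given, some MP-513 subjects may also lose control, and equal withdrawal would leave the difference unchanged.

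The likely size is about 0 to 2 subjects, resting wholly on the assumed rates. It concerns descriptive tables without formal tests (SAP 8.8) and has no effect on the primary HbA1c analysis. It merits correction because any imbalance would probably favour MP-513 on a named safety endpoint.

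**What to change.** 1. In SAP 6.8.1.1, state a TEAE end day tied to the existing 14-day collection window, and apply the same end day to hypoglycaemic episodes.
2. In SAP 7.3, define the point of discontinuation and say whether the sentence applies to safety data, so that it agrees with SAP 6.8.1.1.
3. Derive a flag for any AE or hypoglycaemic episode with onset on or after the first day of another anti-diabetic drug, using the concomitant medication information already collected, including at the follow-up call. State how missing or partial start dates are handled.
4. In SAP 8.8.1, keep the all-events count and show hypoglycaemia and the TEAE overview with and without flagged events.

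The cost is one derived flag and one extra row in each affected display. No change to subject management or visits is involved. That the medication start date is recorded is an assumption to confirm, since the documents say only that concomitant treatment is reviewed. The row without flagged events has slightly shorter follow-up that depends on glycaemic control, so it should stand beside the all-events count and not replace it.

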6.8.1.2 Classifications

Severity:

Severity of AE or hypoglycaemia episode will be graded as “Mild”, “Moderate” or “Severe”. For AEs or hypoglycaemia episodes with missing severity, the most severe assessment will be imputed for summary analyses.

Causal relationship to study drug:

Causal relationship of AE or hypoglycaemia episode to study drug will be graded as “Reasonable possibility” or “No reasonable possibility”. Any missing relationship of an AE or a hypoglycaemia episode to study drug will be considered as “Reasonable possibility”, following the worst case principle.

Cardiovascular Events:

AEs will be adjudicated whether the AE is cardiovascular event or not. That information will be recorded in the CRF.

6.8.2 Clinical Laboratory Evaluations

Clinical laboratory parameters to be measured and their units for analysis are shown in the following table.

Table 5 Clinical Laboratory Parameters and Units

Variables		Conventional Units	How to Convert	Units for Analysis
Haematology	Haemoglobin	g/dL	-	g/dL
	Haematocrit	%	-	%
	Red blood cell count	$\times 10^6/\mu\text{L}$	Multiply with 10^2	$\times 10^4/\mu\text{L}$
	White blood cell count	$\times 10^3/\mu\text{L}$	Multiply with 10^2	$\times 10/\mu\text{L}$
	Platelet count	$\times 10^3/\mu\text{L}$	Divide by 10	$\times 10^4/\mu\text{L}$
Blood Chemistry	AST	U/L	-	U/L
	ALT	U/L	-	U/L
	Gamma-glutamyl transferase (GGT)	U/L	-	U/L
	Lactate dehydrogenase (LDH)	U/L	-	U/L
	Alkaline phosphatase	U/L	-	U/L
	Total bilirubin	mg/dL	-	mg/dL
	Total cholesterol	mg/dL	-	mg/dL

Variables	Conventional Units	How to Convert	Units for Analysis	
Blood Chemistry	Triglycerides	mg/dL	-	mg/dL
	Low-density lipoprotein cholesterol (LDL-C)	mg/dL	-	mg/dL
	High-density lipoprotein Cholesterol (HDL-C)	mg/dL	-	mg/dL
	Blood urea nitrogen	mg/dL	-	mg/dL
	Creatinine	mg/dL	-	mg/dL
	Uric acid	mg/dL	-	mg/dL
	Total protein	g/dL	-	g/dL
	Albumin	g/dL	-	g/dL
	Globulin	g/dL	-	g/dL
	Albumin/globulin ratio	-	-	-
	Direct bilirubin	mg/dL	-	mg/dL
	Creatine kinase	U/L	-	U/L
	Sodium	mEq/L	-	mEq/L
	Potassium	mEq/L	-	mEq/L
	Chloride	mEq/L	-	mEq/L
	Calcium	mg/dL	-	mg/dL
Magnesium	mg/dL	-	mg/dL	
Phosphate	mg/dL	-	mg/dL	
Urinalysis	Glucose	-	-	-
	Protein	-	-	-
	Occult blood	-	-	-
	Urobilinogen	-	-	-
	Ketone bodies	-	-	-
	pH	-	-	-

Any value "Lower Limit of Quantification", e.g. "< x.xx" will be analysed as numerical value "x.xx".

Females of childbearing potential will have serum pregnancy test.

6.8.3 Vital Signs

Vital signs assessment includes measurement of systolic and diastolic blood pressure (mmHg), pulse rate (beats/min), body temperature (celcius) and height (cm).

6.8.4 Electrocardiogram (ECG)

Standard 12- Lead ECG will include recording PR-interval (ms), RR-interval (ms), QRS-interval (ms), QT-interval (ms), QTc (ms) and heart rate (beats/min).

ECGs will be assessed by the Investigators and graded as:

- normal
- abnormal, not clinically significant
- abnormal, clinically significant

6.8.5 Physical Examination

This evaluation will include an examination of general appearance, head, eyes, ears, nose and throat, skin, neck, lungs, cardiovascular, breast, lymph nodes, abdomen, musculoskeletal, neurological and other. These examinations will be categorized as normal or abnormal by the investigator.

7 STATISTICAL METHODS

7.1 General Methodology

All analyses will be performed after the database is locked and access has been removed from the database and the study treatment codes are unblinded.

All statistical tests will be two-sided with a significance level of $\alpha=0.05$, unless specified otherwise and will be performed using SAS® Version 9.2 or higher.

Statistical tests will be supported by presenting estimates and 95% confidence intervals (CI) for the respective treatment effects and differences between the treatment groups. These estimates, confidence intervals and p-value will be based on the respective statistical models used for the analysis.

Data will be summarized using descriptive statistics (number of non-missing values [n], mean, standard deviation [SD], median, minimum, and maximum) for continuous variables and using frequency counts and percentage for discrete variables.

For the purpose of display, the summary results will be rounded as follows:

- Min and Max: same number of decimals as the raw data.
- Mean and Median: one more decimal place than the raw data.
- SD/Standard Error (SE): one more decimal places than the raw data.
- Percentages will be displayed with one decimal precision. A zero count will not have the associated percentage presented on the table (i.e. no 0%).
- All p-values will be displayed with a leading zero except when the value is 1. All p-values will be displayed to four decimal places. If a p-value is less than 0.0001, then the value will be displayed as '<0.0001'. If a p-value is 1, then the value will be displayed as 1.0000. If the p-value cannot be calculated for any reason, the value listed will be 'NA'.
- CI: one more decimal place than the raw data.

For categorical variables with missing values, a category documenting the frequency of missing values will be displayed in the summary tables.

Subject listings of all data from the CRFs as well as any derived variables will be presented. Safety listings of clinical laboratory, vital signs and ECG will be presented by planned visit.

7.2 Adjustments for Covariates

The efficacy variable being analysed will be adjusted for its baseline value, as a covariate in the model.

